## **8.5.3 Combined ECG and clinical endpoints**

### **8.5.3.1 Incidence of aborted myocardial infarction**

The incidence of aborted myocardial infarction will be analyzed using a relative risk as described in Section 8.5.1.

### **8.5.3.2 Need for rescue PCI/revascularization in Group A**

The number of patients who needed rescue PCI/revascularization and the corresponding percentage will be reported. Both the investigator and adjudicated data will be reported.

## **8.5.4 Angiographic endpoints**

### **8.5.4.1 TIMI flow at first coronary angiography**

The number of patients with TIMI flow 0 or 1, 2 and 3 will be reported and percentage will be calculated on those for which a TIMI flow measurement was available. The comparison between the treatment groups will be performed by the Cochran–Armitage test for trend.

### **8.5.4.2 TIMI flow at last coronary angiography**

TIMI flow at last coronary angiography will be analysed similarly as Section 8.5.4.1.

In case only one coronary angiography was performed, the TIMI flow measurement will be used for both the first and the last coronary angiography.

## **8.6 Efficacy Secondary Endpoints**

With the exception of successful reperfusion, the efficacy secondary endpoints will be analyzed using a relative risk as the efficacy clinical endpoint of primary interest (see Section 8.5.1).

For rehospitalization, the reasons reinfarction and CHF will be considered as cardiac reasons, stroke/ICH and other as non-cardiac reasons.

Successful reperfusion 60-90 minutes after injection of tenecteplase will be reported in group A (overall and according to adjudicated rescue status) by numbers and a percentage.

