5.3.2 Evaluations at 1 year

- All-cause mortality:

The patient's vital status at day 365 has to be evaluated. In case of the patient's death between

day 31 and day 365, the date and primary cause of death will be collected retrospectively at the 1-year follow up.

- Rehospitalisation:

If a patient is readmitted to the hospital for cardiovascular reasons between day 31 up to and including day 365, the date(s) and primary reason(s) must be recorded in the eCRF.

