6.1 VISIT SCHEDULE

The trial consists of the following periods:

- Pre-PCI hospital: screening/baseline assessments, informed consent, randomisation, early study treatment
- In-PCI hospital period: continuation of trial treatment as necessary
- Discharge: pre-discharge assessments
- End of trial (day 30): check for AEs and rehospitalisations
- 1-year follow-up: check for vital status and rehospitalisations for cardiovascular reasons.

All assessments per visit are listed in the Trial Flow Chart and are described in section 6.2 and, in more detail, section 5.

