6.2.3.2 Follow-up

Data for the 1-year follow up should be collected at day 365 (up to and including day 395). The required evaluations may be assessed via phone (if a physical visit is not performed) or can also be obtained from medical records.

The following data will be collected at 1-year: vital status/all-cause mortality and rehospitalisation for cardiovascular reasons (since day 30).

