APPENDIX A: CLINICAL EVENTS TO BE RECORDED IN ECRF

Cardiac events within 30 days

- All-cause mortality
- Cardiac mortality
- Cardiogenic shock
- Congestive heart failure
- Recurrent myocardial infarction
- Stent thrombosis
- Rehospitalisation for cardiac reasons
- Rehospitalisation for non-cardiac reasons

Safety events with 30 days

Total stroke, intracranial haemorrhage, ischaemic stroke, haemorrhagic conversion within 30 days

- Procedure related major bleeds (within 48 hours)
- Non-intracranial bleeds (major, minor) and need for blood transfusions up to 30 days

Evaluations at 1 year

- All-cause mortality

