Aborted myocardial infarction⁵⁴ will be assessed by means of ECG as ST-segment resolution relative to baseline value and cardiac marker enzymes as done previously in STREAM-1⁵⁵. Peak levels of troponin I/T (CK/CK-MB) will be collected at baseline, and 8-12 hrs and 24 hrs after randomisation. Quantification of aborted myocardial infarction will be defined as troponin values \leq 5 times the upper limit of normal (ULN) within 24 hours of randomisation (or CK/CK-MB levels \leq 2 times ULN). Only peak values of markers of necrosis (expressed as times exceeding the upper limit of normal) will be recorded in the eCRF; the complete set of measured values will however be kept in the source documents.

Rescue PCI post PPI therapy

If ST-segment resolution is $<50\%$ relative to the ST-segment elevation in the qualifying lead at baseline, irrespective of the presence or absence or clinical symptoms

Refractory ischaemia

Symptoms of ischaemia with ST-deviation or definite T-wave inversion persisting for at least 10 min despite medical management while in-hospital and not fulfilling the diagnosis of infarction.

Major arrhythmias

Sustained ventricular tachycardia (ventricular tachycardia lasting ≥ 30 seconds or requiring cardioversion or causing symptoms/hypotension), ventricular fibrillation, asystole, atrial fibrillation, 2nd and 3rd degree atrio-ventricular block.

Invasive procedures

Include CABG, PTCA, stent placement, intra-aortic balloon.

Other major cardiac events

Other major cardiac events include sustained hypotension, acute mitral regurgitation, acute ventricular septum defect, pericarditis, pulmonary embolism and tamponade.

Sustained hypotension

SBP < 90 mmHg for > 30 minutes

Rehospitalisation for cardiac reasons

If, after discharge, a patient is readmitted to the hospital until day 30 due to cardiac reasons, this information must be recorded in the eCRF. Any event requiring unscheduled readmission will be considered a serious adverse event (SAE) and recorded as described in section 5.2.1. Only if readmission was scheduled, e.g. because of a routine or planned procedure, will the event leading to rehospitalisation not be considered as a serious adverse event.

Rehospitalisation for non-cardiac reasons

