Data about any rehospitalisation for non-cardiac reasons occurring after discharge from initial hospitalisation until day 30 will be collected in the eCRF and have to be recorded on SAE reports in accordance with section 5.2.1. Only if rehospitalisation was scheduled, e.g. because of a routine or planned procedure, will it not be considered as a serious adverse event.

Statistical analysis of clinical events

The analysis will be described in detail in the statistical analysis plan. Clinical events of interest will be assessed as single or composite endpoints for evaluation. All statistical tests on clinical events are of exploratory nature based on descriptive statistics for formal statistical hypotheses generation. For comparison the same composite clinical event rates as in STREAM-1 will be analysed (see APPENDICES). The primary comparisons will be based on the differences between Group PhI and PPCI. Differences between groups and their 95% CI will be calculated. Should a statically significant difference appear in at least one clinical endpoint, i.e. the corresponding CI excludes 0 (no difference), and if there is also consistency for the other endpoints, then this will be considered evidence for a clinically meaningful difference between treatments which should be confirmed in a later study. Should no statistically significant difference be apparent, the CI will be examined to determine to what level a worse outcome can be excluded as has been done with the primary endpoint in STREAM-1.

A formal interim analysis will be performed after 50 % of the planned recruitment. The aim of this analysis is to evaluate the usefulness and feasibility of enlarging the study based on the results.

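### SAP 8.6 labels every readmission other than reinfarction or CHF as non-cardiac, and the SAP analyses non-cardiac readmission to 1 year although only cardiovascular readmissions are collected after day 30

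*SAP*

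**What the plan says.** **Classification.** SAP 6.2 lists cardiac and non-cardiac rehospitalisation as secondary efficacy endpoints at day 30. SAP 8.6 then assigns the reasons: "the reasons reinfarction and CHF will be considered as cardiac reasons, stroke/ICH and other as non-cardiac reasons". Protocol Appendix B, section B2, describes the cardiac endpoint only in general terms: "If, after discharge, a patient is readmitted to the hospital until day 30 due to cardiac reasons". The same section lists other cardiac diagnoses: "Other major cardiac events include sustained hypotension, acute mitral regurgitation, acute ventricular septum defect, pericarditis, pulmonary embolism and tamponade". It also names refractory ischaemia and, under major arrhythmias, ventricular tachycardia and fibrillation, atrial fibrillation and second- or third-degree AV block.

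**Collection.** To day 30, Protocol 6.2.3.1 gathers every rehospitalisation, and Appendix B says of the non-cardiac ones: "Data about any rehospitalisation for non-cardiac reasons occurring after discharge from initial hospitalisation until day 30 will be collected in the eCRF". After day 30 the scope narrows. Protocol 5.3.2 asks for the date and primary reason "If a patient is readmitted to the hospital for cardiovascular reasons between day 31 up to and including day 365". Protocol 6.1 describes the 1-year contact as a "check for vital status and rehospitalisations for cardiovascular reasons", and Protocol 6.2.3.2 has the same restriction. Appendix A places "Rehospitalisation for non-cardiac reasons" among the events within 30 days and lists only all-cause mortality at 1 year.

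**Analysis at 1 year.** SAP 6.5.2 lists both cardiac and non-cardiac rehospitalisation. SAP 8.9.2 analyses both to day 365 with cumulative incidence functions, Gray's test and a relative risk, with death as the competing event. Patients without an event are censored at day 365 or at last follow-up. Table 14.1.2 has a row for each endpoint.

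**The concern.** There are two separate faults.

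The first is labelling. The SAP rule leaves no category for a cardiac reason other than reinfarction or CHF. At day 30 the cardiac endpoint is too narrow, and the non-cardiac endpoint contains cardiac admissions. Both are reported with a relative risk and p-value under labels that readers will take at face value.

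The second is a collection gap. An endpoint covering a full year is planned on data whose scope shrinks after day 30. An admission that was never asked about is indistinguishable in the dataset from one that did not happen, so the analysis treats it as absent. SAP section 5 excludes the section 6.5 endpoints from imputation, and imputation could not in any case recover events that nobody sought.

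Counting stroke/ICH as non-cardiac is a defensible choice and is not criticised here.

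**Working it through.** The plan gives no rehospitalisation rate, power or event count, so there is no planned figure to reproduce. The check sets the SAP rules against the protocol's collection rules.

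| Window | Protocol collects | SAP reports as non-cardiac |
|---|---|---|
| To day 30 | All readmissions (6.2.3.1, Appendix B) | Stroke/ICH and every reason except reinfarction and CHF (8.6) |
| Day 31 to 365 | Cardiovascular readmissions only (5.3.2, 6.1, 6.2.3.2) | Non-cardiac rehospitalisation, continuing to day 365 (6.5.2, 8.9.2, Table 14.1.2) |

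**Length of the gap.** Days 31 to 365 inclusive: 365 − 30 = 335 days. Share of the 1-year window: 335 / 365 = 0.918, or 91.8%. This is a share of calendar time, not of readmissions.

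**Three patients, traced through the rules.**

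1. *Readmitted before day 30 with tamponade, not recorded as reinfarction or CHF.* Protocol Appendix B treats tamponade as a major cardiac event. Under SAP 8.6 the reason falls into *other* and is counted as non-cardiac. The data were collected; only the label is wrong.
2. *Readmitted once, after day 30, for a non-cardiovascular cause.* The protocol text does not ask for this admission. Under SAP 8.9.2 the patient has no event and is censored at day 365 or last follow-up (or has the competing event, if death occurs). The 1-year non-cardiac curve omits exactly the type of event it is named for.
3. *Readmitted after day 30 with an arrhythmia.* This is cardiovascular and is collected. SAP 8.9.2 states no classification of its own. If the 8.6 rule is carried over, the admission counts as non-cardiac.

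Under that carry-over, the only post-day-30 events that can enter the non-cardiac curve are cardiovascular ones: stroke/ICH, arrhythmia, angina and similar. The 1-year curve would then join all-cause-type collection to day 30 with a purely cardiovascular remainder, and the 1-year cardiac endpoint would lose every cardiac admission that is not reinfarction or CHF. The SAP does not say whether the rule carries over. The collection gap exists either way.

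**The case against.** **Flow chart.** The protocol flow chart marks a rehospitalisation check at 1 year without naming a type, so non-cardiovascular admissions might have been recorded. The inconsistency is real and must be reconciled. An unspecific mark does not, however, outweigh three sections that name the type. Protocol 6.1 refers the reader from the flow chart to sections 6.2 and 5 for detail, and both say cardiovascular.

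**Unseen eCRF.** The SAP rule reads like a mapping of fixed form categories, and the form is not in the documents. Nobody can say from the text how many readmissions sit under *other*, or whether that field carries a usable description. This stands. It limits any statement about size and requires a fallback label, but it does not make the present label correct.

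**Softness of the cardiac list.** Appendix B defines cardiac events rather than reasons for readmission, and its list includes pulmonary embolism and sustained hypotension, so it is not a clean dictionary of cardiac readmissions. That is fair. But arrhythmia, AV block, pericarditis and tamponade are not borderline, and the protocol's own definition of cardiac readmission is not confined to two diagnoses.

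**Importance.** The trial has no confirmatory hypothesis. Rehospitalisation comes last in a list ordered by medical importance, and the 1-year version is among the other endpoints. The rule applies equally to both arms, and no direction of bias can be shown. All of this stands and bears on priority. It does not justify reporting a test and a relative risk for an endpoint whose name does not match its content.

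**Conclusion.** Both faults hold. At day 30 the cardiac/non-cardiac split is mislabelled: all readmissions are collected, but cardiac causes other than reinfarction and CHF are reported as non-cardiac. At 1 year the non-cardiac endpoint is incomplete rather than empty: non-cardiovascular readmissions are not collected on 335 of 365 days, and its cumulative incidence, Gray's test and relative risk cannot measure what they name.

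The collection finding assumes that Protocol 5.3.2, 6.1 and 6.2.3.2 govern over the unspecific flow-chart row. Extending the labelling fault to 1 year assumes that SAP 8.6 carries over to 8.9.2, which is the natural reading but is not written. The number of misclassified or missing readmissions cannot be calculated, and none is assumed. The 30-day composite of death, shock, CHF and reinfarction is unaffected. The SAP should be corrected, but the point does not threaten the trial's main results.

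**What to change.** 1. **SAP 8.6.** Replace the rule with: *Readmissions recorded as other will be classified as cardiac or non-cardiac from the recorded primary reason or coded SAE term, blind to treatment arm and before database lock. The same rule applies in Section 8.9.2.* If the form holds no usable reason, rename the cardiac endpoint rehospitalisation for reinfarction or CHF and its counterpart rehospitalisation for any other reason.
2. **SAP 6.5.2, 8.9.2 and Table 14.1.2.** Confirm against the eCRF what was collected after day 30. If it matches the protocol text, remove the 1-year non-cardiac endpoint, keep non-cardiac rehospitalisation at day 30 only, and report cardiovascular rehospitalisation at 1 year as collected, with the cardiac subset where the recorded reasons allow. State where stroke/ICH belongs, so that those admissions are not lost when the non-cardiac row is removed.
3. **Protocol flow chart.** Reconcile the 1-year rehospitalisation row with sections 5.3.2, 6.1 and 6.2.3.2.

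The cost is SAP wording, a small amount of blinded coding, and one fewer 1-year endpoint. No new data are needed. To day 30, unscheduled readmissions are recorded as SAEs (Appendix B) and adverse events are coded (Protocol 5.5). After day 30, adverse event recording has ended (Protocol 5.2.1), so the coding rests on the primary reason that Protocol 5.3.2 requires.

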## **8.7 Safety Secondary Endpoints**

The safety secondary endpoints will be analyzed using a relative risk as the efficacy clinical endpoint of primary interest (see Section 8.5.1).

## **8.8 Combined Efficacy and safety Endpoints**

All combined efficacy and safety secondary endpoints will be analyzed using a relative risk as the efficacy clinical endpoint of primary interest (see Section 8.5.1).

## **8.9 Other Endpoints**

### **8.9.1 Within 30-days**

Duration of index hospitalization will be compared between treatment groups by means of a t-test or Wilcoxon rank test, whichever is appropriate. The duration in each treatment group will be described using means and standard deviations, or median and interquartile range, whichever is appropriate.

The mean difference or Hodges-Lehman estimator with a 95% confidence interval will be reported, whichever is appropriate..

Patient still in hospital at day 30 will be analysed as 30 days. The proportion of patients still in hospital at 30 days will be reported.

### **8.9.2 Evaluations at 1 year**

All-cause mortality will be estimated using Kaplan-Meier curves. The number of events and the event rate at one year will be presented by treatment group. The relative risk for the treatment effect with a 95% confidence interval and corresponding p-value will be reported. In case no event occurred before day 365, patients are censored at day 365 or the last day of follow-up, whichever occurs first.

Rehospitalizations for cardiac and non-cardiac reasons up to one year will be analyzed using competing risk methodology: the event of interest is the endpoint, death will be considered to be the competing risk, patients without an event before day 365 will be censored at the last day of follow-up or day 365, whichever occurs first. Comparisons of the cumulative incidence function (CIF) curves will be done using Gray's test (Gray, 1988). The number of events and the event rate at day 365 will be presented by treatment group. The relative risk for the treatment effect with a 95% confidence interval and corresponding p-value will be reported. A seed number of 2468 will be used

for the simulation of the Gaussian distribution for the calculation of the standard error for the CIF.

### **8.10 Additional in-hospital events**

The number of events and the percentage with respect to the number of subjects for that item will be reported in each treatment group. A Fisher's Exact test will be performed.

### **8.11 Subgroup Analyses**

Subgroup analyses will be done for the ECG efficacy endpoints and the combined clinical endpoint of 30-day total mortality, congestive heart failure, shock and recurrent myocardial infarction.

A test for interaction between subgroup and treatment group will be performed.

Subgroups:

Age	≤75 years; >75 years
Age	Quartiles of age
Time from symptoms onset to randomization	0–<1 hr; ≥1–<2 hr; ≥2 hr
Infarct location	Anterior; Inferior; Other
Sex	Male; Female
Systolic blood pressure	<100 mmHg; 100–139 mmHg; 140–159 mmHg; ≥160 mmHg
Killip class	I; II–IV
Hypertension	Yes; No
Diabetes	Yes; No
Weight	<60 kg; ≥60–90 kg; ≥90 kg
Place of randomization	Ambulance; community hospital
Q-wave	With/without new Q-waves (for index MI) at baseline
TIMI risk score	<5; ≥ 5
Period of randomization	Before protocol amendment 5; after protocol amendment 5
Type of access	Radial vs femoral

In case multiple infarct locations are present within one patient, the patient will be classified as anterior in case anterior is one of the locations or as inferior otherwise.

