6.2.2.1 Group Phi

Assessment of reperfusion

At the receiving PCI hospital patients should be admitted to either the emergency department, coronary care unit or catheterisation laboratory (as per local practice) to assess reperfusion.

The patient's need for rescue coronary intervention will be assessed by both ECG and evaluation of clinical symptoms 90 min (or earlier if clinically indicated) after injection of tenecteplase. These patients may undergo coronary intervention immediately, if indicated, in accordance with the protocol criteria described below.

An additional ECG should be taken before starting the procedure. If there are clinical or electrocardiographic signs of reperfusion that have occurred after the previous ECG, the planned coronary intervention may be postponed.

Cardiac Catheterisation

- If ST-segment resolution is $\geq 50\%$ in the qualifying lead (that had the maximum initial ST-segment elevation in the baseline ECG), diagnostic coronary angiography (followed by

elective PCI +/- stenting, if indicated) should be performed no sooner than 6 hours, but within 24 hours after administration of tenecteplase. This will be considered as planned catheterisation according to protocol

- If ST-segment resolution is < 50 % relative to the ST-segment elevation in the qualifying lead at baseline, irrespective of the presence or absence of clinical symptoms, rescue coronary intervention should be performed promptly.
- If any of the following indications require coronary intervention (irrespective of previous ST-segment resolution), urgent coronary intervention is indicated at any time:
 - haemodynamic instability (presence of any of the following requiring inotropic support: sustained hypotension, cardiogenic shock, or congestive heart failure)
 - refractory ventricular arrhythmias requiring cardioversion or pharmacological treatment
 - worsening ischaemia
 - progressive or sustained ST-segment elevation which, in the judgement of the investigator, requires immediate coronary intervention

All rescue and urgent coronary interventions will be adjudicated by an independent clinical expert as previously described.¹⁹ Feedback to participating sites regarding adherence to protocol defined indications for rescue will be provided as appropriate.

Further ECG measurements

Further ECG measurements are listed in Table 4.

Table 4: Overview of ECG measurements in Group PhI

Timing of ECG	Location	Reason for ECG

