## **5 Handling of Missing Data**

Best efforts will be made to collect complete data for the clinical endpoints of interest, regardless of whether or not the subject received study drug/treatment. In order to minimize bias and take all randomised patients into the analysis when the proportion of missing data for a specific endpoint is larger than 1%, a multiple imputation analysis will be performed. Only endpoints listed in Sections 6.1 to 6.4, with the exception of the ECG endpoint Sum ST-segment deviation

resolution 30-min post-angiogram/PCI, will be imputed, if necessary. No imputation for the endpoints listed in Section 6.5 will be performed.

The baseline covariates age, sex, assigned treatment, body weight, infarct location (anterior or other), previous infarction, Killip class, heart rate, systolic blood pressure and time from symptom onset to randomisation, hypertension, diabetes, place of randomization, Q-wave, time of randomization (before or after protocol amendment 5), time of randomization to administration of tenecteplase or sheath insertion and type of access together with all single efficacy and safety endpoints, ECG (with the exception of the endpoint Sum ST-segment deviation resolution 30-min post-angiogram/PCI) and angiographic endpoints will be multiply imputed using the fully conditional specification (FCS) method using a regression or logistic regression model, whichever is applicable. Note that for the ECG endpoint successful reperfusion, the imputation will be done on the ST-segment resolution from which successful reperfusion will be determined. For mortality, the variables cardiac and non-cardiac mortality instead of overall mortality will be used. For non-intracranial bleeds, only the variables major and minor non-intracranial bleeds will be put in the model. Total non-intracranial bleeds will be determined later on. For stroke, the variables total stroke, will be put in the model. The subclassifications of ischaemic, intracranial haemorrhage, fatal, non-fatal, disabling, non-disabling will be done in a second phase in which the type will be imputed by a random draw from a binary distribution with a probability of success equal to the maximum of the observed event rate or 0.01 stratified by assigned treatment

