**Table 15.2 Additional in-hospital events (PPS)**

**Table 16.1 Subgroup analyses (FAS)**

**Table 16.1.1 All cause death or shock or CHF or reinfarction within 30 days by subgroups (FAS)**

All cause death or shock or CHF or reinfarction within 30 days	PhI (N=#)	P-PCI (N=#)	Relative Risk	P-value	PhI Better	P-PCI Better
Overall event rate	n/N (%)	n/N (%)	#	#		
Age [years] (P=x.xxxx)						
<=75	n/N (%)	n/N (%)	#	#		
>75	n/N (%)	n/N (%)	#	#		
Age [years] (P=x.xxxx)						
< Q1	n/N (%)	n/N (%)	#	#		
Q1-<Q2	n/N (%)	n/N (%)	#	#		
Q2-<Q3	n/N (%)	n/N (%)	#	#		
>=Q3	n/N (%)	n/N (%)	#	#		
Time to randomisation [hours] (P=x.xxxx)						
0-<1	n/N (%)	n/N (%)	#	#		
≥1-<2	n/N (%)	n/N (%)	#	#		
≥2	n/N (%)	n/N (%)	#	#		
Infarct location (P=x.xxxx)						
Anterior	n/N (%)	n/N (%)	#	#		
Inferior	n/N (%)	n/N (%)	#	#		
Other	n/N (%)	n/N (%)	#	#		

All cause death or shock or CHF or reinfarction within 30 days	PhI (N=#)	P-PCI (N=#)	Relative Risk	P-value	PhI Better	P-PCI Better
Sex (P=x.xxxx)						
Male	n/N (%)	n/N (%)	#	#		
Female	n/N (%)	n/N (%)	#	#		
Systolic blood pressure [mmHg] (P=x.xxxx)						
<100	n/N (%)	n/N (%)	#	#		
100-139	n/N (%)	n/N (%)	#	#		
140-159	n/N (%)	n/N (%)	#	#		
≥ 160	n/N (%)	n/N (%)	#	#		
Killip Class (P=x.xxxx)						
I	n/N (%)	n/N (%)	#	#		
II-IV	n/N (%)	n/N (%)	#	#		
Hypertension (P=x.xxxx)						
Yes	n/N (%)	n/N (%)	#	#		
No	n/N (%)	n/N (%)	#	#		
Diabetes						
Yes	n/N (%)	n/N (%)	#	#		
No	n/N (%)	n/N (%)	#	#		
Weight [kg] (P=x.xxxx)						
<60	n/N (%)	n/N (%)	#	#		
≥60-90	n/N (%)	n/N (%)	#	#		
≥90	n/N (%)	n/N (%)	#	#		
Place of randomization (P=x.xxxx)						
Ambulance	n/N (%)	n/N (%)	#	#		
Community hospital	n/N (%)	n/N (%)	#	#		

All cause death or shock or CHF or reinfarction within 30 days	PhI (N=#)	P-PCI (N=#)	Relative Risk	P-value	PhI Better	P-PCI Better
Q-wave (P=x.xxxx)						
With new Q-waves (for index MI) at baseline	n/N (%)	n/N (%)	#	#		
Without new Q-waves (for index MI) at baseline	n/N (%)	n/N (%)	#	#		
TIMI risk score (P=x.xxxx)						
<5	n/N (%)	n/N (%)	#	#		
≥ 5	n/N (%)	n/N (%)	#	#		
Time of randomization (P=x.xxxx)						
Before protocol amendment 5	n/N (%)	n/N (%)	#	#		
After protocol amendment 5	n/N (%)	n/N (%)	#	#		
Type of access (P=x.xxxx)						
Radial	n/N (%)	n/N (%)	#	#		
femoral	n/N (%)	n/N (%)	#	#		

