***Table 16.1.3 Aborted myocardial infarction by subgroups (FAS)***

Similar to 16.1.1

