***Table 16.2 Subgroup analyses (PPS)***

***Table 16.2.1 All cause death or shock or CHF or reinfarction within 30 days by subgroups (PPS)***

***Table 16.2.2 Successful reperfusion by subgroups (PPS)***

***Table 16.2.3 Aborted myocardial infarction by subgroups (PPS)***

***Figure 17.1 Kaplan-Meier curve for all cause death or shock or CHF or reinfarction (FAS)***

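### SAP 8.11 tests treatment interaction with access route (radial or femoral), which is chosen after randomisation and, for the 30-day composite, possibly after the event itself

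*SAP*

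**What the plan says.** SAP 8.11 plans subgroup analyses for the ECG efficacy endpoints and for the 30-day composite of death, shock, heart failure and reinfarction: "A test for interaction between subgroup and treatment group will be performed". The last of the 15 factors is type of access, "Radial vs femoral". Table 16.1.1 prints it in the same layout as the others, "Type of access (P=x.xxxx". The tables for successful reperfusion and aborted infarction are marked "Similar to 16.1.1". The per-protocol series, which begins with "Table 16.2.1 All cause death or shock or CHF or reinfarction within 30 days by subgroups (PPS", mirrors the full-analysis-set tables. That makes six tables.

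SAP 5 introduces its list of imputation variables as baseline covariates. The list ends with "time of randomization to administration of tenecteplase or sheath insertion and type of access".

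Protocol 6.2.2.1 sets three routes to catheterisation in PhI. After adequate ST resolution, angiography "should be performed no sooner than 6 hours, but within 24 hours after administration of tenecteplase". After inadequate resolution, rescue is prompt. Urgent intervention is indicated at any time for, among other reasons, "haemodynamic instability (presence of any of the following requiring inotropic support: sustained hypotension, cardiogenic shock, or congestive heart failure". In the primary PCI (PPCI) arm, catheterisation is the index treatment. Protocol 4.1.5 states that treatment is open-label. Neither document gives a rule on access route.

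On cut points, SAP 8.11 and Table 16.1.1 split age at ≤75 and >75. SAP Table 2.1, both pooled elderly sets and SAP 10 split at <75 and ≥75. The two upper weight bands in 8.11 both contain 90 kg. SAP 3 and Protocol 7.5 speak of pooling the ≥70 group with STREAM-1, while the pooled sets in SAP 4 use ≥75.

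**The concern.** A comparison of arms within a subgroup is protected by randomisation only if membership was fixed beforehand. Route is not: an operator who knows the arm chooses it, hours after randomisation in much of PhI, and at a different kind of procedure in each arm. If femoral access goes with higher risk more strongly in one arm than in the other, the relative risks in the two strata differ even when no patient has a treatment effect. A real interaction can be hidden in the same way.

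The row would stand beside 14 factors that are essentially pre-randomisation, with the same kind of P-value and nothing to mark the difference. (Killip class may exceptionally be recorded on hospital arrival, according to Protocol 5.2.1.) In a hypothesis-generating trial, a misleading interaction is something that could be carried forward.

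**Working it through.** **1. Order of events, by endpoint**

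| Endpoint (full analysis and per-protocol sets) | Can it precede the choice of route? |
|---|---|
| 30-day composite | Yes. In PhI, shock or heart failure requiring inotropic support is both an urgent trigger (Protocol 6.2.2.1) and an instance of a composite component (SAP 6.1.1). |
| Successful reperfusion | No. It is read 30 minutes after angiogram or PCI (SAP 6.1.2). |
| Aborted infarction | Not settled by the documents. It uses ECG and marker values over the first 24 hours, which overlap the PhI catheterisation window. |

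The lack of randomisation applies to all six tables. Membership that follows the outcome is documented for the composite, so for two of them.

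**2. Possible size.** The plan states no figure to reproduce. From the documents: 400 PhI and 200 PPCI; an 18 to 20% composite rate in STREAM-1 patients ≥60 (Protocol 7.5), taken here as 19% in both arms with no effect in anyone; rescue share r of 25 to 30% (Protocol 5.3.3). All access shares and risk ratios are assumptions. Let c be the femoral-to-radial risk ratio within an arm. Then femoral RR ÷ radial RR = c(PhI) ÷ c(PPCI).

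*Rescue.* Let rescue patients have k = 1.5 to 2.5 times the risk of scheduled patients, with femoral shares (scheduled/rescue) of 10/20, 10/30 or 15/25%. The scheduled risk is p0 = 0.19/(1 − r + rk).
- Low end (r = 0.25, k = 1.5, 15/25%): p0 = 0.169, femoral risk 0.199, radial 0.188, c = 1.06.
- High end (r = 0.30, k = 2.5, 10/30%): p0 = 0.131, femoral risk 0.242, radial 0.180, c = 1.34.
- With c(PPCI) assumed between 1.00 and 1.34, the ratio of RRs runs from 1.06/1.34 = 0.79 to 1.34/1.00 = 1.34. It is 1.00 when c is equal in both arms.

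*Shock or heart failure before catheterisation.* Let a share u = 1 to 4% of PhI have such an event first, with femoral access in 20 to 30% of them and 10 to 20% of the rest. The others have risk (0.19 − u)/(1 − u).
- Example (u = 4%, 30% against 10%): the others' risk is 0.15/0.96 = 0.156. Femoral risk is (0.04×0.30 + 0.96×0.10×0.156)/(0.04×0.30 + 0.96×0.10) = 0.027/0.108 = 0.250. Radial risk is 0.163/0.892 = 0.183, so c = 1.37.
- The ratio of RRs is 1.03 to 1.37 if no PPCI patient has such an event, 1.01 to 1.15 if half as many do, and 1.00 if equally many do.

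**3. Precision of the row.** For femoral share f, SE(log ratio) = √[(0.81/0.19)(1/(400f) + 1/(400(1−f)) + 1/(200f) + 1/(200(1−f)))].

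| f (assumed) | PPCI femoral patients | Events | SE | 95% CI around 1 |
|---|---|---|---|---|
| 10% | 20 | 3.8 | 0.596 | 0.31–3.22 |
| 20% | 40 | 7.6 | 0.447 | 0.42–2.40 |
| 30% | 60 | 11.4 | 0.390 | 0.47–2.15 |

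In 200,000 simulated trials per setting, with f from 10 to 30%, a two-sided 5% Wald test flags a ratio of 1.00 in 2.9 to 4.7%, 1.34 in 2.8 to 10.5% and 1.5 in 4.3 to 17.2%.

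**4. Imputation list.** Neither route nor time to tenecteplase or sheath insertion is a baseline variable, and the second measures a different interval in each arm. SAP 5 says that the listed covariates are multiply imputed along with the endpoints. It also restricts imputation to endpoints of Sections 6.1 to 6.4, less one ECG endpoint. It is silent on patients never catheterised, for whom no route exists.

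**5. Cut points.** If age is held in whole years and 2 to 5% of patients are 75 (assumed), 600×0.02 = 12 to 600×0.05 = 30 patients count as younger in Table 16 and elderly in the pooled set. With exact age, almost none do. Date of birth is recorded (Protocol 6.2.1), but the SAP does not say how age is computed.

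**The case against.** The strongest reply is that little hangs on this row. The trial has no confirmatory hypothesis, every test is exploratory, and no decision rests on the access subgroup. The flag rates above stay near or below 5% in most settings. The main illustration does not even fix a direction. This stands, and it limits severity. The exploratory label does not make route a baseline factor, though, and a row this imprecise also loses little by going.

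Three stronger readings are tempting and not supported:

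- *The row is likely to show a false interaction.* False-flag rates of 7 to 41% can be produced, but only by assuming that 30 to 50% of PhI composite events precede sheath insertion against 10% in PPCI, with femoral access rising from 20% to between 50 and 70% after an event. None of these shares is in the documents. With equal early shares the rate stays at 4 to 5%.
- *The outcome can define the subgroup in all six tables.* Successful reperfusion is always read after the procedure. The PhI trigger is also narrower than any shock or heart failure, because it needs inotropic support.
- *The SAP will impute a route for patients who never had one.* Section 5 contradicts itself on whether covariates are imputed, and imputation runs only when an endpoint is more than 1% missing. Post-randomisation variables may legitimately serve as predictors in an imputation model. The baseline label is a wording error, and the handling of uncatheterised patients is a gap.

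**Conclusion.** The point holds in limited form. The interaction test on access route compares arms within strata formed after randomisation, in all six tables. For the composite, in the full analysis and per-protocol sets, stratum membership can follow the event. No other section of the protocol or SAP repairs this.

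Size and direction are unknown. The illustrative range of 0.79 to 1.37 rests on assumed access shares, assumed risk ratios and a common 19% event rate, and it collapses to 1.00 if route relates to risk alike in both arms. Severity is low to moderate.

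A reader might infer that the overall comparison in SAP 8.5.1 is compromised. It is not: the unadjusted relative risk and risk difference compare the arms as randomised, do not use route, and need no change on this account. The age and weight cut points are small alignment edits, and the age one matters only if age is in whole years.

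**What to change.** - **SAP 8.11, Tables 16.1.1–16.1.3 and 16.2.1–16.2.3:** delete type of access. If it is kept, label it descriptive and post-randomisation, with no interaction P-value.
- **Tables 7.1 and 7.2:** add a row for route by arm among catheterised patients and, in PhI, by scheduled against rescue or urgent procedure.
- **SAP 5:** stop calling route and time from randomisation to tenecteplase or sheath insertion baseline covariates. Reconcile the covariate list with the sentence that limits imputation to the endpoints of 6.1 to 6.4. Do not impute route or sheath time for patients never catheterised. The simplest way is to leave both variables out of the imputation model. A separate category for no route would not work: those patients have no TIMI flow and no post-angiogram ST resolution, so its coefficient cannot be estimated in the models for these endpoints.
- **Cut points:** use <75 and ≥75 in 8.11 and the Table 16 series, state how age is computed, and write the middle weight band as ≥60 to <90 kg.
- **Pooling:** record the ≥75 pooled set as a departure from the ≥70 sentence in both SAP 3 and Protocol 7.5. Rewriting only the SAP sentence would leave it at odds with the protocol. The ≥75 cut does fit the STREAM-1 dose reduction described in Protocol 1.1.

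The cost is SAP wording, one row removed or relabelled in six tables, one descriptive row added to two, and a short note on the pooled set. No new data are needed.
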